#### 10.3.2 Site/Investigator questionnaire

Not applicable

#### 10.3.3 Participant tracking log (if applicable)

In all countries, two different enrolled patient identification logs will be documented: one specific log for patients who signed an informed consent form, another specific one for dead patients, lost to follow up patients and for alive patients who did not visit the site during the data collection period. At the time of the database lock, and before the analysis, the specific enrolled patient identification log documented for dead patients, lost to follow up patients and for patients who did not visit the site during the data collection period and where the unique identifier is documented will be destroyed by the site. Therefore, collected data will not be identifiable for these patients.

#### 10.4 PROCEDURE AND CONSEQUENCE FOR PARTICIPANT WITHDRAWAL FROM STUDY

Protocol template for disease observational studies				
			Research and Development	
QSD-003149	Disease observational study protocol v. 6.0	with disease Application Date (DD/MM/YYYY) : dd-Mmm- 09/11/2020	EFFECTIVE	

<DD-MM-YYYY HH:mm:ss> < 15-01-2021 21:03:21 > UTC

primary data collection  
Study Number: GER-CAD-19-11180

Version number: ~~V6~~V7.0

Patients can withdraw from the study at any time, without giving a reason and without any penalty or loss of benefits to which they are otherwise entitled and without any effect on their future medical care. Should consent be withdrawn, data already collected up to the date of consent withdrawal will continue to be processed, but no new data will be collected.

Property of the Sanofi-Aventis Groupe - strictly confidential

Protocol template for disease observational studies					
				Research and Development	
QSD-003149	Disease observational study	with disease	Application Date (DD/MM/YYYY) :dd-Mmm-09/11/2020	EFFECTIVE	
protoco v. 6.0yyyy		<del><DD-MM-YYYY HH:mm:ss> <15-01-2021 21:03:21 > UTC</del>			

Formatted: Left, Tab stops: 8,89 cm, Centered + 17,1 cm, Right

primary data collection  
 Study Number: GER-CAD-19-11180                      Version number: ~~V6~~V7.0

## 11 MANAGEMENT OF DATA

### 11.1 DATA COLLECTION, VALIDATION AND DATA QUALITY CONTROL AT CERNER ENVIZA LEVEL

Data will be entered at the site by the treating physician or an authorized staff member, into the electronic case report forms (eCRFs), which will be administered through the study Electronic Data Capture (EDC) system. Data will be entered into eCRFs in accordance with eCRF instructions. Each study investigator has ultimate responsibility for the collection and reporting of all data entered on the eCRFs and for ensuring that they are accurate, authentic / original, complete, consistent, and legible. Only authorized personnel will have access to the eCRF.

An eCRF should be completed for each subject. The completed eCRFs are the sole property of Sanofi-Aventis Groupe and should not be made available in any form to third parties, except for authorized representatives of Sanofi-Aventis Groupe or appropriate regulatory authorities, without written permission from Sanofi-Aventis Groupe. Any corrections to entries made in the eCRFs must be dated, initialed and explained (if necessary) and should not obscure the original entry. The eCRFs must be signed or approved by the study investigator or by an authorized staff member to attest that the data contained in the eCRFs is true.

All electronic data collection material hosted on the secure study web portal in European Union will include programming of electronic data checks, edit checks depending on data previously entered and automatic queries to make sure that the core variables are provided, and that the data entered is within a plausible range.

The computerized handling of the data by Cerner Enviza may generate additional requests to which the participating Investigator is obliged to respond by confirming or modifying the data questioned.

Data from the eCRFs will be compiled into a single, pseudo-anonymized dataset. Data collection and validation procedures will be detailed in appropriate operational documents.

Protocol template for disease observational studies				
			Research and Development	
QSD-003149	Disease observational study protocol v. 6.0	with disease yyyy	Application Date (DD/MM/YYYY) :dd-Mmm- 09/11/2020	EFFECTIVE

<DD-MM-YYYY HH:mm:ss> < 15-01-2021 21:03:21 > UTC

primary data collection  
Study Number: GER-CAD-19-11180

Version number: ~~V6~~V7.0

## 11.2 MONITORING AND DATA QUALITY CONTROL AT SITE LEVEL

During study conduct, Cerner Enviza (or their designee) will perform routine remote oversight of the sites' data collection activities and may also conduct periodic on-site monitoring visits ~~(except in Germany where no on-site visit will be conducted)~~ to ensure that the protocol is being followed. If applicable, during on-site visits, the monitors may review source documents to confirm that the data recorded is accurate. All information recorded in the study eCRFs must be consistent with the patients' source documentation (i.e., medical records).

Data entered into the database will be verified/validated as documented in components of the data management plan (DMP). Data cleaning specifications will include consistency and plausibility checks on data, as well as rules for data handling (e.g., process for query creation/closure, process for listing data review, process for missing and non-conformant data review, process for data handling and validation of electronic records; process for medical coding of data, process for collection of investigator signature, process for freeze/lock of the clinical database).

Property of the Sanofi-Aventis Groupe - strictly confidential

Protocol template for disease observational studies				
			Research and Development	
QSD-003149	Disease observational study protoco v. 6.0	with disease yyyy	Application Date (DD/MM/YYYY) :dd-Mmm- 09/11/2020	EFFECTIVE

<DD-MM-YYYY HH:mm:ss> < 15-01-2021 21:03:21 > UTC

Formatted: Left, Tab stops: 8,89 cm, Centered + 17,1 cm, Right

primary data collection  
Study Number: GER-CAD-19-11180

Version number: ~~V6~~V7.0

## 12 PHARMACOVIGILANCE

The study is a non-interventional, descriptive, retrospective study based on secondary data collection from medical records of patients.

The design of such studies is characterized by secondary use of data previously collected from consumers or healthcare professionals for other purposes. Examples include medical chart reviews (including following-up on data with healthcare professionals), analysis of electronic healthcare records, systematic reviews, meta-analyses.

For these studies, the submission of suspected adverse reactions in the form of ICSRs (Individual Case Safety Reports) is not required. All adverse events/reactions collected for the study should be recorded and summarized in the interim safety analysis and in the final study report unless the protocol provides for different reporting with a due justification (see GVP Module VIII).

Protocol template for disease observational studies					
				Research and Development	
QSD-003149	Disease observational study	with disease	Application Date (DD/MM/YYYY) : dd-Mmm-	EFFECTIVE	
	protoco v. 6.0yyyy		09/11/2020		

<DD-MM-YYYY HH:mm:ss> < 15-01-2021 21:03:21 > UTC

primary data collection  
Study Number: GER-CAD-19-11180

Version number: ~~V6~~V7.0

### 13.2 DISPOSITION OF PARTICIPANTS

The following data will be presented to describe the patients' disposition:

- Number and percentage of patients belonging to the analysis population.

### 13.3 ANALYSIS POPULATIONS

Analysis population contains all patients who met the inclusion criteria and none of the exclusion criteria and were documented into the study.

### 13.4 STATISTICAL METHODS

This study is primarily descriptive in nature and does not include formal statistical hypothesis testing. A formal statistical analysis plan (SAP) that will provide details of all analyses and presentation of study data will be approved prior to database lock. All final analyses will be performed once the data from all patients has been collected in the database, cleaned and database lock has occurred.

All variables will be summarized descriptively through tabular displays of mean, median, ranges and standard deviations (SD) of continuous variables and frequency distributions of categorical variables. Changes in disease activity closest to the date of each study event will be described, where data are available. Crude incidence rates (with 95% CI) will be calculated from the number of TE after CAD diagnosis and the sum of individual person-years contributed by the CAD population during the study period. The mortality rate will also be estimated in this way. For event analysis, the main events evaluated will include time to first TE and time to death. The cumulative incidence of TE will be estimated using Kaplan-Meier survival analysis accounting for mortality as a competing risk event if sample size allows it. Descriptive analysis will be used to identify risk factors associated with occurrence of TE.

Protocol template for disease observational studies				
			Research and Development	
QSD-003149	Disease observational study	with disease	Application Date (DD/MM/YYYY) : dd-Mmm-09/11/2020	EFFECTIVE

<DD-MM-YYYY HH:mm:ss> < 15-01-2021 21:03:21 > UTC

primary data collection  
Study Number: GER-CAD-19-11180

Version number: ~~V6~~V7.0

Due to the potentially variable length of follow-up, HCRU will be calculated as per-patient-per-month (PPPM) during the variable follow-up period of up to 12 months after the TE diagnosis. Patients with both “confirmed” and “presumed” CAD will be included in the primary analysis. Sensitivity analysis will be performed to address any potential misclassification in CAD diagnosis; patients who fully meet the inclusion criteria will be classified as having “confirmed CAD”; reported patients who were diagnosed with CAD but whose medical records do not capture all the data required to define CAD or distinguish CAD vs CAS using strict haemato-immunologic diagnosis criteria will be classified as “presumed CAD”.

Depending on scientific interest and the distribution of the data, exploratory analyses may be conducted to examine other research questions, *e.g.* TE-free survival curves may be derived for individuals with none versus one or more CAD-related TE risk factors.  
A specific analysis will be conducted for Italy.

Patients’ records will not be excluded because of missing data, and missing data will not be imputed. The base relevant to each analysis will be reported alongside the percent of missing data in tables provided for all descriptive analyses.

As the data are analysed, some deviation from planned analysis may be anticipated (*e.g.*, missing data, small sample size). Therefore, the SAP may modify the plans outlined in the protocol; any major modifications would be reflected in a protocol amendment.

All statistical analyses will be carried out using standard statistical software, including SAS, Stata, R as appropriate.

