#### CAD and risk of thromboembolic events (TEs)

Recent data suggest a correlation between CAD and thromboembolic events (TEs), which can impact quality of life and also lead to premature mortality (14, 15). TEs can also substantially increase disease burden and cost of treatment in CAD; in the general population, ten to thirty percent of patients die within 1 month of diagnosis of a venous thrombotic event (VTE), and among those who survive, 50% have long-term complications (16). An incident VTE has been estimated to cost between \$12 000 and \$15 000 in 2014 in the USA, which increased to \$18 000-\$23 000 when including subsequent complications (17).

Nevertheless, TE data in CAD is sparse, and the rarity of CAD limits the ability to perform large population-based studies. Several methodological limitations should be considered when interpreting existing TE data from the largest population-based studies in CAD and TE; a retrospective study in the USA involving a cohort of 608 individuals diagnosed with CAD from an insurance-based registry and nearly 6,000 matched controls recorded (venous and arterial) TE

Property of the Sanofi-Aventis Groupe - strictly confidential

Protocol template for disease observational studies					
				Research and Development	
QSD-003149	Disease observational study	with disease	Application Date (DD/MM/YYYY) : dd-Mmm- 09/11/2020	EFFECTIVE	

<DD-MM-YYYY HH:mm:ss> < 15-01-2021 21:03:21 > UTC

Formatted: Left, Tab stops: 8,89 cm, Centered + 17,1 cm, Right

primary data collection  
Study Number: GER-CAD-19-11180

Version number: ~~V6~~V7.0

during a 10-year period in 30 percent of those with CAD versus 18 percent of controls (adjusted hazard ratio [HR], 1.94; 95% confidence interval [CI], 1.64-2.30) (18), but misclassification due to coding errors inherent to claims data is likely. A smaller study from a Danish registry found an increased rate of TE in CAD patients as compared with age- and sex-matched controls (19), but there were also some methodology issues associated with the lack of validation of diagnostic codes in such registry.

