## 10 DATA COLLECTION

### 10.1 DATA COLLECTION SCHEDULE

Pseudo-anonymized epidemiologic, clinical, and biologic data from patient's medical charts will be extracted by site staff from the initial date of CAD diagnosis until the earliest of death, end of data availability (*i.e.* lost to follow-up) or end of data collection set on January 1st, 2020. Diagnosis must have occurred between January 1st, 2009 and January 1st, 2019. Duration of follow-up will depend on time of diagnosis; a priori, enrolled patients diagnosed earlier during this time period will have a longer follow-up period than those diagnosed later. There will be no minimum duration of follow-up. However, HCRU analysis will require having data from patient medical records available for a minimum of time following a TE to ensure all costs associated with each TE are covered. Per-patient-per-month (PPPM) HCRU will be calculated during the variable follow-up period of up to 12 months after the TE diagnosis.

There will be no prospective follow-up period. No examinations or procedures apart from those occurring as part of the patient's routine clinical care are required for this study.

The schedule of events is described in Table 2: Schedule of Recommended Study Assessments

Since this study is retrospective in nature, results will be collected as available.

Table 2: Schedule of Recommended Study Assessments

Data to be collected	Assessments	Screening	Baseline	Follow-up
Eligibility criteria		X		
Written informed consent (IC)		X		
Demographics			X	
Medical History	Comorbidities; TE risk factors		X	X
CAD diagnosis history and disease status	Clinical findings; indicators of anemia and hemolysis		X	X

Property of the Sanofi-Aventis Groupe - strictly confidential

Protocol template for disease observational studies					
				Research and Development	
QSD-003149	Disease observational study	with disease	Application Date (DD/MM/YYYY) : dd-Mmm-09/11/2020	EFFECTIVE	

<DD-MM-YYYY HH:mm:ss> < 15-01-2021 21:03:21 > UTC

Formatted: Left, Tab stops: 8,89 cm, Centered + 17,1 cm, Right

primary data collection  
Study Number: GER-CAD-19-11180

Version number: ~~V6~~V7.0

Significant medical events	TE dates and types; previous history of TE		X	X
Relevant treatment history	CAD-specific treatment patterns; response to treatment		X	X
Direct HCRU related to TE	Hospitalizations and length of stay; outpatient, ER and ICU visits			X
Patient vital status	Cause of death; date of death			X

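### A single PPPM rate over unequal post-TE windows does not correct for short follow-up, and the minimum window in section 10.1 has no length and no rule for early deaths

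*Protocol*

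**What the plan says.** The synopsis and sections 10.1 and 13.4 make the same choice. Section 13.4 gives unequal follow-up as the reason for it: "HCRU will be calculated as per-patient-per-month (PPPM) during the variable follow-up period of up to 12 months after the TE diagnosis". Records are abstracted "until the earliest of death, end of data availability" or 1 January 2020.

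Section 10.1 first says "There will be no minimum duration of follow-up" for the study as a whole. It then makes an exception: "HCRU analysis will require having data from patient medical records available for a minimum of time following a TE", in order to "ensure all costs associated with each TE are covered". No length is given for that minimum, section 13.4 and the synopsis do not repeat it, and nothing is said about patients who die before reaching it.

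Section 13.4 says that all variables will be "summarized descriptively through tabular displays of mean, median, ranges and standard deviations". It does not say whether PPPM is an average of each patient's own rate or total contacts over total patient-months. The HCRU outcomes in Table 1 are the percentage of patients with each contact type, length of stay and number of procedures.

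Section 5.1 notes that in the general population "ten to thirty percent of patients die within 1 month of diagnosis" of a venous event.

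**The concern.** Dividing by observed time adjusts for unequal follow-up only when use is spread evenly over that time. The admission, intensive care and procedures for an acute TE fall at the start of the window. A patient who dies in week two has much the same acute care as one followed for a year, but a far smaller denominator. The same TE then looks more resource-intensive the sooner follow-up stops.

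The undefined minimum can do harm in the other direction. If it is used as an entry condition, patients who die early leave the HCRU analysis, and they may be among the most severe cases. Neither reading meets the aim in section 10.1 of covering all costs of each TE. Section 5.2 says that the results will inform HTA dossiers, where a PPPM figure may be read as the resource burden of a TE.

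**Working it through.** The protocol states no HCRU figure, so there is none to reproduce.

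**Inputs from the protocol.** Window of up to 12 months, ended by death, loss to follow-up or 1 January 2020 (10.1, 13.4). TE patients: 20–30% of 170 = 34–51 (13.1). One-month mortality of 10–30% (5.1).

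**Assumptions.** One admission at the TE, plus λ = 0–0.08 further admissions per month. The 10–30% mortality, a general-population VTE figure, is applied to all TEs in CAD; deaths are uniform within month 1, then 1% per month. Diagnosis is uniform over 2009–2019 with a constant TE hazard. Minimum window: none, 1 or 3 months.

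**Step 1, one patient.** PPPM = 1/t for one admission in t months: 0.083 at 12 months, 0.33 at 3 months (4 times), 1.0 at 1 month (12 times).

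**Step 2, how often windows are short.** Deaths in month 1: 10% of 34 to 30% of 51, about 3 to 15 patients. For the data cut, the number at risk rises linearly over the ten diagnosis years (area 10/2 = 5) and is flat in 2019 (area 1). The share of TEs with less than 12 months to the cut is therefore 1/(5+1) = 17%.

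**Step 3, target.** Twelve-month use per TE patient, expressed per month = (1 + λM)/12, where M is mean months alive in the year. With one-month mortality d, M = 0.5d + (1−d)[1 + (1−e^−0.11)/0.01] = 0.5d + 11.417(1−d), which is 10.33 at d = 10% and 8.14 at 30%. The target is 0.083 at λ = 0, and 0.152 or 0.138 at λ = 0.08.

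**Step 4, the two possible estimators.** With window w, the mean of patient rates is E(1/w) + λ and the pooled rate is 1/E(w) + λ. E(1/w) was simulated. E(w) follows from the assumptions.

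| Minimum | E(1/w) | E(w), months | Mean of rates too high by | Pooled too high by | TE patients dropped |
|---|---|---|---|---|---|
| 1 month | 0.120 | 10.63 | 31–45% | 13–27% | 11–31% |
| 3 months | 0.098 | 11.05 | 17–29% | 9–24% | 15–34% |
| None | unstable | 9.49 (d = 10%), 7.49 (d = 30%) | several-fold | 22–60% | 0 |

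Examples with a 1-month minimum at λ = 0.08: mean of rates 0.200/0.152 = 1.31 and 0.200/0.138 = 1.45; pooled (1/10.63 + 0.08)/0.138 = 0.174/0.138, about 1.27 before rounding. Pooled with no minimum, d = 30%, λ = 0: (1/7.49)/0.083 = 1.60. In the simulation, 75–96% of the dropped patients had died; the rest were cut by 1 January 2020.

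**Step 5, no minimum.** If windows can approach zero, E(1/w) has no finite value, so the simulated mean depends on the shortest window allowed. At λ = 0.03 and d = 10% it is 0.41 with a 7-day floor and 0.64 with a 1-day floor, against a target of 0.109.

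**Step 6, control.** When all use occurs at a constant rate, the mean of patient rates is unbiased (simulated 0.0835, true 0.0833). The overstatement comes from early concentration of use, not from PPPM as such.

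**The case against.** The strongest reply is that the protocol has a safeguard and leaves the estimator open. Section 10.1 does require some minimum post-TE time. PPPM can equally mean total contacts over total patient-months, and section 13.4 defines its incidence and mortality rates in that pooled way. The median is also planned and is less sensitive to short windows. Details may be in the SAP, which is not shown. The mortality input comes from VTE in the general population.

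Much of this stands. A reader might infer that windows of any length are allowed, that patient-level rates will be averaged, and that the mean must be 5 to 15 times too high. The documents support none of these: a minimum is stated, averaging is not, and a multiple of that kind depends on an arbitrary shortest window. A reader might also infer that PPPM has to deliver the Table 1 percentages. Nothing says so; section 13.4 plans frequency distributions, which would supply them.

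The reply does not remove the point. The pooled rate is a valid rate per month observed, yet it still overstates 12-month use per TE patient, because early deaths contribute the acute admission and few months. A minimum limits inflation only by excluding those deaths. The median describes a typical patient, not total resource use. The single PPPM over a variable window, with unequal follow-up as its reason, is stated in the protocol itself, not left for the SAP.

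**Conclusion.** The point holds as a flaw in a stated rule for a secondary, descriptive outcome. One PPPM rate over unequal post-TE windows does not do what section 13.4 wants it to do. With a 1- or 3-month minimum, the overstatement of 12-month use is about 17–45% for a mean of patient rates and about 9–27% for a pooled rate. With no minimum, the pooled rate is about 22–60% too high and the mean of patient rates is several-fold too high and unstable. A minimum used as an exclusion would drop about 11–34% of TE patients, mainly early deaths.

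These sizes rest on one admission per TE, 0–0.08 further per month, and the transferred 10–30% mortality. Lower early mortality in CAD would shrink the pooled error and the exclusions. The direction depends only on care being concentrated at the event.

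**What to change.** Amend 13.4, 10.1 and the synopsis as follows.

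- Keep patients who die early in the HCRU analysis, and replace the open-ended minimum with censoring at end of data.
- Report mean cumulative contacts and hospital days per TE patient to 12 months, treating death as the end of use. Show month 1 and months 2–12 separately.
- If PPPM is kept, compute it as total contacts over total patient-months within each of these two periods. Some distortion remains in month 1: with 30% dying uniformly in that month and one admission each, the rate is 1/(1 − 0.3 × 0.5) = 1.18. The cumulative figure is therefore preferable.
- Give the percentage of patients with each contact type at fixed horizons of 1 and 12 months.

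The contact dates are already collected (section 10.3.1, items 6.1–6.4). The cost is wording in three places, a little more programming, and less direct comparability with publications that report a single PPPM.
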